2.3. Background for Correlative Studies

2.3.1. Functional Imaging

Functional tumor imaging with dynamic contrast enhanced magnetic resonance imaging (DCE-MRI) is capable of evaluating changes in vascularity and quality of index lesions. This imaging modality takes advantage of the fact that angiogenic vessels are hyperpermeable to many macromolecules by assessing the kinetics of contrast inflow and egress from a tumor region of interest. Quantitative parameters such as the volume of transfer constant of contrast agent (K_{trans}) or the blood plasma volume fraction (v_p) as well as semi-quantitative measures, such as area under

[figure not shown]
the contrast concentration versus time curve for 90 seconds after contrast injection (IAUC₉₀) can be derived from DCE-MRI studies. This modality may provide early indications of treatment effect even before changes in size can be perceived on CT. The molecular imaging studies will be performed for research purposes and will not be used to assess clinical responses as defined by RECIST criteria.

2.3.2. Cytokine Modulation

Most of the inhibitors of angiogenesis, direct and indirect, are associated with altered regulation of proangiogenic and proinflammatory cytokines. These pharmacodynamic changes are consistent across different modalities of angiogenesis inhibition and include induction of circulating VEGF, IL6, IL8, angiopoietin2, and others. To date, these endpoints have not been validated as predictive or prognostic for ovarian cancer response to angiogenesis inhibitors. Economopoulou and colleagues demonstrated that functional γ H2AX is required for cell response to aggravated hypoxia indicating a need for DNA repair in angiogenesis NAT MED. Thus, it is posited that there will be greater differences in the pharmacodynamic cytokine response to the combination of cediranib and olaparib.

2.3.3. PAR Incorporation

Incorporation of polyADP ribose moieties at sites of double stranded DNA breaks is a signal to the repair machinery to initiate repair. It is not a marker of repair, per se. It was initially hypothesized that modulation of PAR incorporation by PARP inhibitors would be both proof of mechanism and could be used to predict outcome. Proof of mechanism was shown in an early phase 0 study of ABT-888 (veliparib) by Kummar et al (Kummar *et al.*, 2009) but predictive or prognostic value has not been reported. Preliminary analysis of PBMC PAR incorporation data from the NCI phase 1 study of olaparib and carboplatin suggests that initial PAR incorporation results may be predictive of response to the combination. Those preliminary data using pretherapy results are provocative and form the basis for examining PBMC PAR concentrations as an exploratory endpoint in this study.

Lee, Hays, and [name] and colleagues evaluated the potential of incorporation of PAR at baseline into PBMC in BRCA1/2^{mut} women accrued to a study of olaparib and carboplatin. ROC analysis of initial PAR levels in each patient measured against her response (PR/CR vs. PD) indicated a

cutoff of 190.5pg PAR/1x10⁷ PBMC would yield a sensitivity of 50% and specificity of 100%. This cutoff value was then applied to the evaluable patient cohort (N=29) for stratification prior to comparison with PFS and Wilcoxon analysis. A trend toward increased PFS was observed for patients with initial levels of PAR incorporation in PBMCs less than the ROC-predetermined cutoff (p=0.08; HR 2.05).

2.4. Rationale

The treatment of recurrent ovarian cancer with conventional cytotoxic agents is unsatisfactory. Combinations of novel agents with demonstrated effects in ovarian cancer may improve clinical outcome. Results from studies of cediranib and other anti-angiogenic agents have demonstrated single-agent activity in ovarian cancer. Olaparib has demonstrated single-agent activity in BRCA-deficient ovarian cancer and other cells deficient in homologous recombination. Studies have shown that BRCA wild-type ovarian cancers still demonstrate deficiencies in homologous recombination, and studies of olaparib as monotherapy in BRCA wild-type ovarian cancers are ongoing.

2.4.1. Rationale for Selected Approach and Trial Design

- Treatment of recurrent ovarian cancer with conventional cytotoxic agents is limited by development of chemoresistance and intolerable side effects. New therapeutic approaches are needed to improve clinical outcomes.
- Studies of cediranib and other anti-angiogenic agents have demonstrated single-agent activity in ovarian cancer.
- Olaparib is a PARP-1 inhibitor that is active against BRCA-deficient ovarian cancer. It is also active against cells deficient in homologous recombination (HR) in the in vitro setting.
- BRCA wild-type ovarian cancers still demonstrate deficiencies in the homologous recombination pathways. PARP-1 inhibitors have also demonstrated activity in BRCA wild-type ovarian cancers, potentially due to other mechanisms conveying HR-deficiency.
- BRCA-deficient and triple-negative breast cancers share a similar molecular profile in tissue microarrays (Sorlie et al., 2003, Lakhani et al., 2002).
- PARP-inhibition has demonstrated anti-angiogenic effects in preclinical studies. Incubation of endothelial cells with PJ-34 (a PARP inhibitor) inhibited proliferation of the cells (Pyriochou et al., 2008). GPI 15427 (a potent PARP-1 and PARP-2 inhibitor) inhibits in vivo angiogenesis in a matrigel plug assay. PARP-1 knockout mice also demonstrate decreased in vivo angiogenesis by matrigel plug assay when compared with control mice with wild-type PARP-1 activity (Tentori et al., 2007).
- The combination of cediranib and olaparib has the potential for synergistic effect, given the anti-angiogenic effects of PARP-inhibition, while having minimal overlapping toxicities.

As cediranib and olaparib have not been used in combination with one another before, a Phase I dose escalation study will first be completed to determine the MTD of these two agents in

combination. The MTD would be considered the recommended Phase 2 dose (RP2D). The study would then evaluate the effectiveness of the RP2D of the combination of cediranib and olaparib as compared to that of cediranib alone in platinum-sensitive recurrent papillary-serous ovarian, fallopian tube, and peritoneal cancers. The single agent dose of cediranib has been determined to be 30mg daily, and olaparib has been studied in ovarian cancer at a dose of 400mg twice daily in a capsule formulation. Due to concerns regarding the overlapping toxicity of fatigue or unexpected toxicities in setting of combining these two agents for the first time, the starting dose of cediranib will be 20mg daily and that of olaparib will be 100mg twice daily.

3. Participant SELECTION

3.1. Inclusion Criteria

Potentially eligible patients will be screened by their gynecologic oncologist and/or medical oncologist. Participants must meet the following criteria on screening examination to be eligible to participate in the study:

- 3.1.1. For Phase I Portion:** Participants must have histologically or cytologically confirmed epithelial ovarian cancer, primary peritoneal serous cancer, fallopian tube cancer, or triple-negative breast cancer.

For Phase II Portion: Participants must have histologically or cytologically Grade 2 or 3 (high-grade) papillary-serous or endometrioid epithelial ovarian cancer, primary peritoneal serous cancer, or fallopian tube cancer. Participants with epithelial ovarian, primary peritoneal, or fallopian tube cancers of other high-grade histologies who carry a known deleterious BRCA germline mutation by standard clinical testing (Myriad BRCAAnalysis) will also be considered eligible.

For Phase I-T Portion: Participants must have histologically or cytologically confirmed epithelial ovarian cancer, primary peritoneal serous cancer, or fallopian tube cancer.

- 3.1.2.** Ovarian cancer, primary peritoneal, and fallopian tube participants in the Phase 1 and Phase 1-T portions of this trial must have either measurable cancer by RECIST 1.1 criteria or an elevated CA125 level at least twice the upper limit of normal on two separate occasions at least 1 day but not more than 3 months apart. At least one of the samples should be within 1 week of starting treatment. Patients with both an elevated CA125 and measurable cancer will be followed by RECIST 1.1 criteria. Patients with only an elevated CA125 level will be followed by modified GCIG criteria, as detailed in Section 10.2.

Participants in the Phase II portion of the trial must have measurable disease by RECIST 1.1 criteria.

Breast cancer participants must have measurable disease by RECIST criteria.

- 3.1.3.** Prior therapy:

For Phase I and Phase I-T Portions:

- Prior chemotherapy for ovarian cancer patients must have included a first-line platinum-based regimen with or without intravenous consolidation chemotherapy.
- Breast cancer patients must have recurred post both an adriamycin- and taxane-containing regimen.
- Prior hormonal-based therapy for ovarian, primary peritoneal serous, fallopian tube cancer, or breast cancer is acceptable.

- Patients may not have had a prior PARP-inhibitor in the recurrent or metastatic setting. Prior treatment with BSI-201 is allowed.
- Patients may not have had a prior anti-angiogenic agent in the recurrent or metastatic setting.

For Phase II Portion:

- Prior chemotherapy must have included a first-line platinum-based regimen with or without intravenous consolidation chemotherapy.
- Prior hormonal-based therapy for ovarian, primary peritoneal serous, or fallopian tube cancer is acceptable.
- Patients may not have previously received a PARP-inhibitor. Prior treatment with BSI-201 is allowed.
- Patients may not have had a prior anti-angiogenic agent in the recurrent setting.
- Patients may have received up to 1 non-platinum-based line of therapy in the recurrent setting.
- Patients may have received an unlimited number of platinum-based therapies in the recurrent setting.
- Patients should have platinum-sensitive disease, where platinum-sensitive disease is defined as having had a > 6 month interval since last receiving platinum therapy prior to disease recurrence. Patients must have had a prior response while on the platinum-containing regimen and cannot have experienced disease progression while receiving platinum.

Subjects may begin cediranib and olaparib at least 3 weeks after their last dose of chemotherapy or hormonal therapy, assuming they are otherwise eligible.

- 3.1.4.** Age \geq 18 years. Because no dosing or adverse event data are currently available on the use of cediranib or olaparib in participants < 18 years of age, children are excluded from this study but will be eligible for future pediatric trials.
- 3.1.5.** Estimated life expectancy of greater than 6 months.
- 3.1.6.** ECOG performance status 0 or 1 (Karnofsky > 60%, see Appendix A).
- 3.1.7.** Participants must have adequate organ and marrow function as defined below:
- Absolute neutrophil count \geq 1,500/mcL
 - Platelets \geq 100,000/mcL
 - Hemoglobin > 9 g/dL
 - For patients enrolled to the Phase 1-T portion of the protocol, the Hemoglobin should be \geq 10 g/dL
 - Total bilirubin within 1.5 times the upper limit of normal institutional limits
 - AST (SGOT)/ALT (SGPT) \leq 2.5 \times institutional upper limit of normal
 - Creatinine \leq the institutional upper limit of normal or creatinine clearance \geq 60 mL/min/1.73 m² for subjects with creatinine levels above institutional normal

- Less than or equal to 1+ proteinuria on two consecutive dipsticks taken no less than 1 week apart, or < 1 gm protein on 24-hour urine collection or a urine protein:creatinine ratio of < 1.
 - Troponin T or I within normal institutional limits
 - Coagulation parameters (INR, aPTT) within 1.25 × upper limit of normal institutional limits, except where a Lupus anti-coagulant has been confirmed
- 3.1.8.** Toxicities of prior therapy (excepting alopecia) should be resolved to less than or equal to Grade 1 as per NCI-CTCAE v4.0 (located on the CTEP website at http://ctep.cancer.gov/protocolDevelopment/electronic_applications/ctc.htm. Patients with long-standing stable grade 2 neuropathy may be considered after discussion with the overall PI.
- 3.1.9.** Subjects with treated limited stage basal cell or squamous cell carcinoma of the skin or carcinoma in situ of the breast or cervix are eligible. Subjects with prior cancer treated with a curative intent with no evidence of recurrent disease 5 years following diagnosis and judged by the investigator to be at low risk of recurrence are eligible. Subjects with any other concomitant or prior invasive malignancies are ineligible.
- 3.1.10.** Patients who have the following risk factors are considered to be at increased risk for cardiac toxicities. These patients should have increased monitoring (see study calendar Section 9.0)
- Prior treatment with anthracyclines
 - Prior treatment with trastuzumab
 - A New York Heart Association classification of II controlled with treatment (see Appendix E)
 - Prior central thoracic radiation therapy (RT), including RT to the heart
 - History of myocardial infarction within 12 months (Patients with history of myocardial infarction within 6 months are excluded from the study).
- 3.1.11.** The effects of cediranib and olaparib on the developing human fetus are unknown. For this reason, women of child-bearing potential and men must agree to use adequate contraception (hormonal or barrier method of birth control; abstinence) prior to study entry, for the duration of study participation, and for 3 months following treatment discontinuation. Should a woman become pregnant or suspect she is pregnant while participating in this study, she should inform her treating physician immediately.
- 3.1.12.** Ability to understand and the willingness to sign a written informed consent.
- 3.1.13.** Patients must be able to tolerate oral medications and not have gastrointestinal illnesses that would preclude absorption of cediranib or olaparib.
- 3.1.14.** Patients must be willing and able to check and record daily blood pressure readings.

3.2. Exclusion Criteria

Participants who exhibit any of the following conditions at screening will not be eligible for admission into the study.

- 3.2.1.** Participants who have had chemotherapy or radiotherapy within 3 weeks (6 weeks for nitrosoureas or mitomycin C) prior to entering the study or those who have not recovered from adverse events due to agents administered more than 3 weeks earlier.
- 3.2.2.** Participants may not be receiving any other investigational agents nor have participated in an investigational trial within the past 4 weeks. Subjects may not have received prior treatment affecting the VEGF pathway in the recurrent setting, including thalidomide, bevacizumab, sunitinib, or sorafenib. In the Phase I portion of the trial, subjects may not have received prior treatment with oregovomab (OvaRex) or any other antibodies that may interfere with CA-125 measurements.
- 3.2.3.** Patients with untreated brain metastases, spinal cord compression, or evidence of symptomatic brain metastases or leptomeningeal disease as noted on CT or MRI scans should not be included on this study, since neurologic dysfunction may confound the evaluation of neurologic and other adverse events. Screening imaging to rule out brain metastases is not required for screening, but should be performed prior to study enrollment if clinically indicated. Patients with treated brain metastases and resolution of any associated symptoms must demonstrate stable post-therapeutic imaging for at least 6 months following therapy prior to starting study drug.
- 3.2.4.** History of allergic reactions attributed to compounds of similar chemical or biologic composition to cediranib or olaparib.
- 3.2.5.** Participants receiving any medications or substances that are *strong* inhibitors or inducers of CYP3A4 are ineligible. A list of CYP3A4 inhibitors and inducers is provided in Appendix D. Dihydropyridine calcium-channel blockers are permitted for management of hypertension.
- 3.2.6.** Patients with any of the following:
- History of myocardial infarction within six months
 - Patients with QTc prolongation > 500 msec or other significant ECG abnormality noted within 14 days of treatment.
 - For patients enrolled in the Phase 1-T portion of the protocol, the QTc should not exceed 470 msec.
 - NYHA classification of III or IV
 - If cardiac function assessment is clinically indicated or performed: LVEF less than normal per institutional guidelines, or < 55%, if threshold for normal not otherwise specified by institutional guidelines.
 - Condition requiring concurrent use of drugs or biologics with pro-arrhythmic potential (see Appendix F).

- 3.2.7.** History of stroke or transient ischemic attack within six months.
- 3.2.8.** Patients may not have any evidence of pre-existing inadequately controlled hypertension (defined as a systolic BP of >140 mmHg or a diastolic BP of >90 mmHg), and must have a normal blood pressure (\leq 140/90 mmHg) taken in the clinic setting by a medical professional within 2 weeks prior to starting study. Patients with hypertension may be managed with up to a maximum of three antihypertensive medications. Patients who are on three antihypertensive medications must be actively followed by a cardiologist or blood pressure specialist for management of blood pressure while on protocol.
- 3.2.9.** Any prior history of hypertensive crisis or hypertensive encephalopathy
- 3.2.10.** Clinical significant peripheral vascular disease or vascular disease (aortic aneurysm or aortic dissection)
- 3.2.11.** Unstable angina
- 3.2.12.** Major surgical procedure, open biopsy, or significant traumatic injury within 28 days prior to starting cediranib.
- 3.2.13.** History of abdominal fistula, gastrointestinal perforation or intra-abdominal abscess.
- 3.2.14.** Current signs and/or symptoms of bowel obstruction or signs and/or symptoms of bowel obstruction within 3 months prior to starting study drugs.
- 3.2.15.** Current dependency on IV hydration or TPN.
- 3.2.16.** Evidence of coagulopathy or bleeding diathesis. Therapeutic anticoagulation for prior thromboembolic events is permitted.
- 3.2.17.** Uncontrolled intercurrent illness including, but not limited to ongoing or active infection, symptomatic congestive heart failure, unstable angina pectoris, cardiac arrhythmia, or psychiatric illness/social situations that would limit compliance with study requirements.
- 3.2.18.** Pregnant women are excluded from this study because cediranib and olaparib are agents with the potential for teratogenic or abortifacient effects. Because there is an unknown but potential risk of adverse events in nursing infants secondary to treatment of the mother with cediranib and olaparib, breastfeeding should be discontinued if the mother is treated with cediranib or olaparib. These potential risks may also apply to other agents used in this study.
- 3.2.19.** Known HIV-positive individuals are ineligible because of the potential for pharmacokinetic interactions with cediranib or olaparib. In addition, these individuals are at increased risk of lethal infections when treated with marrow-suppressive therapy.

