Tumor markers. Tumor markers alone will not be used to assess response for the phase II portion of this study. If markers are initially above the upper normal limit, they must normalize for a subject to be considered in complete clinical response. Specific guidelines for both CA-125 response (in recurrent ovarian cancer) and PSA response (in recurrent prostate cancer) have been published [JNCI 96:487-488, 2004; *J Clin Oncol* 17, 3461-3467, 1999; *J Clin Oncol* 26:1148-1159, 2008]. In addition, the Gynecologic Cancer Intergroup has developed CA-125 progression criteria which are to be integrated with objective tumor assessment for use in first-line trials in ovarian cancer [JNCI 92; 1534-1535, 2000]. CA-125 response criteria and progression criteria are detailed further in Section 10.2.

Cytology, Histology. These techniques can be used to differentiate between partial responses (PR) and complete responses (CR) in rare cases (e.g., residual lesions in tumor types, such as germ cell tumors, where known residual benign tumors can remain). The cytological confirmation of the neoplastic origin of any effusion that appears or worsens during treatment when the measurable tumor has met criteria for response or stable disease is mandatory to differentiate between response or stable disease (an effusion may be a side effect of the treatment) and progressive disease.

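### The exclusion of antibodies that may interfere with CA-125 names only Phase I, although Phase I-T also admits patients without measurable disease who are followed by CA-125

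*Combined protocol and SAP*

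**What the plan says.** Section 3.2.2 states the exclusion for one portion: "In the Phase I portion of the trial, subjects may not have received prior treatment with oregovomab (OvaRex) or any other antibodies". The full object of the exclusion is "oregovomab (OvaRex) or any other antibodies that may interfere with CA-125 measurements".

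Section 3.1.2 sets the disease requirement for two portions together. For ovarian, primary peritoneal and fallopian tube cancer it reads: "Phase 1 and Phase 1-T portions of this trial must have either measurable cancer by RECIST 1.1 criteria or an elevated CA125 level". To qualify by the marker, a patient needs two CA-125 values that each reach double the normal limit. The section adds: "Patients with only an elevated CA125 level will be followed by modified GCIG criteria, as detailed in Section 10.2".

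For patients without measurable disease, Section 10.2.2 defines response as a confirmed CA-125 fall of at least 50%, and Section 10.2.3 defines progression as a doubling from the pre-treatment value. Section 10.3 makes the CA-125 response, together with no progression on CT, the route to clinical response benefit. Section 1.3.4 lists clinical benefit and PFS among the Phase I-T secondary objectives.

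**The concern.** The protocol names a threat to CA-125 measurement and guards against it in Phase I. The same entry route and the same marker-based follow-up exist in Phase I-T, where no guard is written. A Phase I-T patient who has had one of these antibodies and has no measurable disease could be enrolled, called a responder or declared progressed on values that interference may have shifted. The documents do not say in which direction.

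Two things are at stake: the Phase I-T descriptions of clinical benefit and PFS, and the individual decision to stop, since disease progression ends treatment under Section 5.5.

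**Working it through.** No figure in the plan needs reproducing, and alpha, power and sample size play no part. The check compares sections and then does one line of arithmetic.

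**1. Does Phase I in Section 3.2.2 include Phase I-T?** The eligibility section names both when it means both. Section 3.1.3 heads a block "For Phase I and Phase I-T Portions", and Section 3.1.2 names the two together. The exclusion list also names Phase I-T where a criterion is particular to it: "For patients enrolled in the Phase 1-T portion of the protocol, the QTc should not exceed 470 msec" (Section 3.2.6). On the literal reading, Section 3.2.2 does not reach Phase I-T.

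**2. Does another criterion close the gap?** The remaining parts of Section 3.2.2 are a four-week limit on investigational agents and trials, and a bar on prior VEGF-pathway treatment in the recurrent setting. The Phase I and Phase I-T prior-therapy rules in Section 3.1.3 restrict PARP inhibitors and anti-angiogenic agents. None of these excludes a past antibody that interferes with CA-125.

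**3. Is there a reason to leave Phase I-T out?** There is one for Phase II: it requires measurable disease (Section 3.1.2), and "Tumor markers alone will not be used to assess response for the phase II portion of this study" (Section 10.1.3). Neither reason applies to Phase I-T, and no other is given.

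**4. What rests on the marker for a CA-125-only patient, and what does CT catch?**

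| Step | Rule | Does CT help? |
|---|---|---|
| Entry | Two values at least twice the upper limit (3.1.2) | No |
| Response | Confirmed fall of at least 50% (10.2.2) | Not if CT is stable |
| Clinical benefit | CA-125 response and no CT progression for at least 16 weeks (10.3) | Partly |
| Progression | Doubling from baseline (10.2.3) | Not for a false doubling |
| Staying on study | CA-125 below double baseline, and stable tumor measurements without new lesions (10.2.3) | Yes, for a missed progression |

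PFS is defined in Section 10.4.5 by objective progression, without saying whether a CA-125 doubling counts. Section 10.4.2 treats CA-125 as one way of documenting progression objectively, so I assume that it counts for these patients.

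**5. Size.** Let n be the number of patients in the denominator. One misclassified patient shifts the clinical benefit rate by 100/n percentage points. With the maximum Phase I-T enrolment of 30 (Section 1.1), 100/30 = 3.3 points; a smaller denominator gives a larger shift. If the CA-125-only patients were reported separately and numbered 5 to 10 (my assumption; the documents give no figure), the shift in that subset would be 100/10 = 10 to 100/5 = 20 points. These are shifts per misclassified patient. Per exposed patient they are ceilings, because interference must carry a value across the 50% or doubling threshold before anything is misclassified.

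**The case against.** The strongest reply is that Phase I is sometimes an umbrella term. Section 1.1 calls the tablet part a phase I (tablet) dose escalation portion. Section 10 opens by describing CA-125 follow-up for the phase I component without naming Phase I-T, although Section 3.1.2 sends Phase I-T patients to Section 10.2. On that reading the exclusion already covers them. This stands as a reason to call the defect imprecise scope. It does not remove it, because the eligibility section itself, which the eligibility checklist has to follow, separates the two.

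The second reply is that the consequences are small. The Phase I-T primary endpoint is MTD and DLT (Section 14.1.4), which do not use CA-125. Sections 14.1.2 and 14.1.5 list only toxicities as secondary for Phase I-T, and Section 14.2 plans no Phase I-T efficacy analysis. A CA-125 response needs a confirmatory sample, and the Phase I and Phase I-T calendar schedules CT or MRI every 8 weeks with no exception for CA-125-only patients. All of this stands and limits the weight of the point. It leaves the false doubling, and the false response with stable CT, uncorrected.

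A reader might infer that CA-125 is invalid in every exposed patient, or that clinical benefit and PFS then become uninterpretable. The documents do not support that: Section 3.2.2 says only that these antibodies may interfere, and CT is a partial safeguard.

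**Conclusion.** The gap holds as a minor inconsistency between Sections 3.1.2 and 3.2.2. Read literally, an exposed Phase I-T patient without measurable disease is eligible, and her entry, CA-125 response and CA-125 progression rest on a potentially unreliable marker. The reach is confined to the Phase I-T clinical benefit and PFS objectives in Section 1.3.4 and to stopping for CA-125 progression; the dose-finding conclusion is unaffected.

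The effect on clinical benefit is about 3 points per misclassified patient at 30 enrolled. Neither the size of the CA-125-only group nor the number with prior exposure is given, so the actual effect may be nil. The conclusion rests on the literal reading of the Phase I label and, for PFS, on a CA-125 doubling counting as progression.

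**What to change.** Reconcile Section 3.2.2 with Section 3.1.2 by opening the sentence with *In the Phase I and Phase I-T portions of the trial*, and leave the rest of it as it is. Carry the change into the eligibility checklist.

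The exclusion should not be narrowed to patients followed by CA-125. That would newly admit exposed Phase I patients with measurable disease, for whom an initially raised marker must still normalize before a complete response is called (Sections 10.1.3 and 10.1.4).

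For Phase I-T patients already enrolled, check prior-therapy records, flag any exposed CA-125-only patient, and report clinical benefit and PFS with and without her. A sensitivity analysis suits Section 14.3.2, which bases conclusions on all eligible participants, better than outright removal.

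This is a cheap improvement: a few words, a checklist line and a records check. The downside is a very small narrowing of Phase I-T eligibility. Sample size, power and alpha do not change.
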